12.7 Best Response

12.7.1 Evaluation of Best Overall Response

The best overall response is the best response recorded from the start of the treatment until disease progression/recurrence (taking as reference for progressive disease the smallest measurements recorded since the treatment started). The patient's best response assignment will depend on the achievement of both measurement and confirmation criteria.

Table 6. Sequences of overall response assessments with corresponding best response.

1 st Assessment	2 nd Assessment	Best Response
Progression		Progressive disease
Stable, PR, CR	Progression	Progressive disease
Stable	Stable	Stable
Stable	PR, CR	Stable
Stable	Not done	Not RECIST classifiable
PR	PR	PR
PR	CR	PR
PR, CR	Not done	Not RECIST classifiable
CR	CR	CR

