8.0 EVALUATIONS/MATERIAL AND DATA TO BE ACCESSIONED

8.1 Required Clinical, Laboratory and Disease Evaluation

All clinical and laboratory studies to determine eligibility must be performed within 7 days prior to enrollment unless otherwise indicated. Laboratory values used to assess eligibility (see [Section 4.0](#)) must be no older than seven (7) days at the start of therapy. Laboratory tests need **not** be repeated if therapy starts **within** seven (7) days of obtaining labs to assess eligibility. If a post-enrollment lab value is outside the limits of eligibility, or laboratory values are older than 7 days, then the following laboratory evaluations must be re-checked within 48 hours prior to initiating therapy: CBC with differential, bilirubin, ALT (SGPT) and serum creatinine. If the recheck is outside the limits of eligibility, the patient may not receive protocol therapy and will be considered off protocol therapy. Imaging studies must be obtained within fourteen (14) days prior to start of protocol therapy (repeat the tumor imaging if necessary). See [Appendix XIII](#) for Therapy Delivery Maps for Cycle 1 and all subsequent cycles.

Studies to be Obtained	For all patients		For patients \geq 12 months ONLY	For patients $<$ 12 months ONLY
	Pre-Study	During Cycle 1	Prior to Subsequent Cycles [^]	Prior to Subsequent Cycles [^]
History	X	X	X	X
Physical exam with vital signs ⁷	X	Weekly	X	X
Height, weight, BSA	X		X	X
Performance status	X		X	X
CBC, differential, platelets	X	Twice weekly ¹	Weekly ^{1,2,3}	Weekly ^{1,2,3}
Electrolytes including Ca ⁺⁺ , PO ₄ , Mg ⁺⁺	X	Weekly	X	Weekly
Creatinine	X	Weekly	X	Weekly
ALT, AST, bilirubin	X	Prior to each dose of pevoneditat, then weekly*	Prior to each dose of pevoneditat, then weekly*	Prior to each dose of pevoneditat, then weekly*
ECHO/EKG	X			
Albumin	X		X	X
Pulse Oximetry	X		X	X
Pregnancy test ⁴	X		X	X
Tumor disease evaluation	X	End of Cycle 1	End of Cycle 2 then every other cycle x 2 then q 3 cycles ⁵	End of Cycle 2 then every other cycle x 2 then q 3 cycles ⁵
Bone Marrow Evaluation ⁸	X	End of Cycle 1	End of Cycle 2 then every other cycle x 2 then q 3 cycles ⁵	End of Cycle 2 then every other cycle x 2 then q 3 cycles ⁵
Pharmacokinetics ⁶ (required)	X	X		
Pharmacodynamics (optional)	X	X		
INR	X			

[^] Studies may be obtained within 72 hours prior to the start of the subsequent cycle.

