12.2.5 Overall Response Assessment

Table 2. For Patients with Measurable Disease (i.e., Target Disease)

Target Lesions	Non-Target Lesions	New Lesions	Overall Response	Best Overall Response when Confirmation is Required*
CR	CR	No	CR	≥ 28 days Confirmation
CR	Non-CR/Non-PD	No	PR	≥ 28 days Confirmation
CR	Not evaluated	No	PR	
PR	Non-CR/Non-PD/not evaluated	No	PR	
SD	Non-CR/Non-PD/not evaluated	No	SD	documented at least once ≥ 28 days from baseline
PD	Any	Yes or No	PD	no prior SD, PR or CR
Any	PD**	Yes or No	PD	
Any	Any	Yes	PD	

* See RECIST 1.1 manuscript for further details on what is evidence of a new lesion.
 ** In exceptional circumstances, unequivocal progression in non-target lesions may be accepted as disease progression.

Note: Patients with a global deterioration of health status requiring discontinuation of treatment without objective evidence of disease progression at that time should be reported as “*symptomatic deterioration*.” Every effort should be made to document the objective progression even after discontinuation of treatment.

Table 3. For Patients with Non-Measurable Disease (i.e., Non-Target Disease)

Non-Target Lesions	New Lesions	Overall Response
CR	No	CR
Non-CR/non-PD	No	Non-CR/non-PD*
Not all evaluated	No	not evaluated
Unequivocal PD	Yes or No	PD
Any	Yes	PD

* ‘Non-CR/non-PD’ is preferred over ‘stable disease’ for non-target disease since SD is increasingly used as an endpoint for assessment of efficacy in some trials so to assign this category when no lesions can be measured is not advised

Table 4. Overall Response for Patients with Neuroblastoma and Measurable Disease

CT/MRI	MIBG	Bone Scan	Bone Marrow	Catechol	Overall
PD	Any	Any	Any	Any	PD
Any	PD	Any	Any	Any	PD
Any	Any	PD	Any	Any	PD
Any	Any	Any	PD	Any	PD
SD	CR/PR/SD	Non-PD	Non-PD	Any	SD
PR	CR/PR	Non-PD	Non-PD	Any	PR
CR/PR	PR	Non-PD	Non-PD	Any	PR
CR	CR	Non-PD	Non-PD	Elevated	PR
CR	CR	CR	CR	Normal	CR

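### Table 6 labels stable disease then progression as PD, against the Section 12.7.1 definition, and for measurable disease conflicts with Table 2 on three further sequences

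*Combined protocol and SAP*

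**What the plan says.** Section 12.7.1 opens with the definition: "The best overall response is the best response recorded from the start of the treatment until disease progression/recurrence". Its last sentence before the table makes the assignment "depend on the achievement of both measurement and confirmation criteria". Table 6 then maps pairs of assessments to a best response. SD, PR or CR followed by progression is PD. SD, PR or CR followed by an assessment that was not done is "Not RECIST classifiable".

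Table 2 in Section 12.2.5, headed for measurable (target) disease, has its own best-response column. There PD carries the condition "no prior SD, PR or CR", and SD must be "documented at least once" at 28 days or more from baseline. Tables 3, 4 and 5 and the CNS table in 12.6.7 have no such column.

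Sections 12.2.6, 12.3.6, 12.4.5, 12.5.2 and 12.6.7 all send best response to Section 12.7, and 12.4.5 names Table 6. Confirmatory imaging is required only after PR or CR (Section 8.1, footnote 5; Section 12.2). Section 12.2.1.1 defines a responder separately, as a patient with CR or PR confirmed by central review before non-protocol anti-cancer therapy. Antitumor activity is a secondary aim (1.2.1), and Section 11.5 plans descriptive reporting only.

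**The concern.** Two analysts who both follow the protocol can give the same patient different best responses, depending on whether they apply the definition, Table 2 or Table 6. The sequences are not exotic. Tumor evaluation is due at the end of Cycle 1 and then "End of Cycle 2 then every other cycle x 2 then q 3 cycles", so SD at the first scan and progression at the second is an ordinary course. SD then no assessment can arise when a patient leaves treatment in Cycle 2 for toxicity or refusal. Section 10.1 then asks only for the observations that clinical care needs, and no further tumor evaluation is specified.

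At stake is the split between SD, PD and unclassifiable, which may be much of what a small phase 1 activity summary can show.

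**Working it through.** No planned figure has to be reproduced here. The check sets the three rules side by side.

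**Step 1: expand Table 6.** PD at first assessment (1); SD, PR or CR then PD (3); SD-SD (1); SD-PR and SD-CR (2); SD-not done (1); PR-PR (1); PR-CR (1); PR-not done and CR-not done (2); CR-CR (1). Total 1+3+1+2+1+1+1+2+1 = 13 sequences.

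**Step 2: compare the labels.** Confirmation is taken to apply to CR and PR only, because no passage requires it for SD.

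| Sequence | Table 6 | 12.7.1 definition | Table 2 column (measurable disease) |
|---|---|---|---|
| SD, then PD | PD | SD | SD if at least 28 days from baseline; PD barred by the prior SD |
| PR, then PD | PD | unconfirmed; no category named | PD barred; no category named |
| CR, then PD | PD | unconfirmed; no category named | PD barred; no category named |
| SD, then not done | unclassifiable | no conflict claimed | SD if at least 28 days from baseline |

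The other nine sequences show no conflict of label. PR or CR then not done is among them, because Table 2 gives no rule for it.

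Result under Table 2: 4 of 13 sequences conflict when the SD is at least 28 days from baseline. With an earlier SD, SD-not done drops out. The progression rows still conflict on the literal text, because the Table 2 condition on PD carries no 28-day qualifier. Result outside Table 2: 1 of 13, SD then PD.

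Section 12.7.2 points the same way. It measures SD from the start of treatment until progression, so under Table 6 a patient with SD then PD has a duration of SD but a best response of PD.

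**Step 3: can one scan meet the 28-day condition?** Baseline timing is from Section 8.1: "Imaging studies must be obtained within fourteen (14) days prior to start of protocol therapy". Let L = 0 to 14 be the days from baseline imaging to Day 1. Let d be the cycle day of the end-of-Cycle-1 scan, which may fall in the 72 hours before Cycle 2. The interval is L + (d − 1). The documents imply two start days for Cycle 2, and this check does not choose between them.

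- Start on Day 28 (Appendix XIII-A): d = 25 to 28, so the interval is 24 to 41 days. It is at least 28 days in 11+12+13+14 = 50 of 15 × 4 = 60 day combinations, and always when L is 4 or more.
- Start on Day 29 (Section 5.1 and the design schema treat Day 28 as Day 0 of Cycle 2): d = 26 to 29, so the interval is 25 to 42 days. It is at least 28 days in 12+13+14+15 = 54 of 60, and always when L is 3 or more.

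These count permitted days with no delay to Cycle 2. They are not probabilities. They show only that the schedule lets a single end-of-Cycle-1 SD qualify under Table 2.

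**Step 4: compare with the responder definition.** Section 12.2.1.1 asks for central review and does not itself ask for a second scan. Section 8.2.1 sends patients with CR or PR to central review. On that text, a patient with a centrally confirmed PR who then progresses could be counted as a responder while Table 6 gives a best response of PD.

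**The case against.** The best defence is that Table 6 is a deliberate, stricter convention: a patient must be free of progression at two assessments before any category better than PD is given. The sentence on confirmation criteria lends this some support. The row that labels SD then PR or CR as Stable does not refute it, since that patient is also progression-free at the second assessment. This stands as a possible reading outside Table 2, and it is why the point is less certain there. It does not stand under Table 2, where one SD suffices and PD is excluded after earlier SD, PR or CR. If the stricter convention is intended, the 12.7.1 sentence and the Table 2 column need editing instead.

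It is also fair to object that response is secondary, descriptive and exploratory. That limits the consequence but does not remove the contradiction.

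A reader might infer several stronger things that the documents do not support:

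- That PR or CR then progression should simply become Stable. Table 2 bars PD but names no replacement.
- That PR or CR then progression also contradicts 12.7.1 outside Table 2. The confirmation requirement prevents that claim.
- That the 28-day SD rule covers every disease type. Table 2 is limited to measurable disease, and the Table 3 footnote discourages SD as a label for non-target disease even though 12.3.4 defines it for evaluable disease.
- That every disputed patient is a non-responder whichever label is used. Section 12.2.1.1 does not secure this for PR or CR then progression.

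**Conclusion.** The inconsistency is real and should be corrected before best response is tabulated. For patients under Table 2 it is firm: four of 13 sequences, with SD then not done counted only when the SD is at least 28 days from baseline. For other disease types it is confined to SD then progression and is less certain.

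The consequence is limited to the SD/PD/unclassifiable split in the descriptive activity summary. PR or CR then progression may also bear on consistency with the responder count under 12.2.1.1. MTD, recommended Phase 2 dose and sample size do not depend on Table 6. The documents give no progression rate, so no frequency is claimed. As scale only, one relabelled patient is 1/6 = 16.7 percentage points in a dose level of six, or 1/18 = 5.6 points among the 18 Part A1 patients enrolled by 6/30/19.

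The conclusion rests on reading SD as needing no confirmation, and on keeping Table 2 within its heading. One matter stays open: whether the prior SD that excludes PD in Table 2 must itself meet the 28-day condition.

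**What to change.** For patients under Table 2:

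- Label SD documented at least 28 days from baseline, followed by progression or by no assessment, as Stable.
- Remove PD as the label for PR or CR then progression. State a replacement category that agrees with both Table 2 and the responder definition in 12.2.1.1. The documents do not supply one, so the sponsor has to choose it.
- For SD earlier than 28 days then progression, reconcile the unqualified prior-SD condition on PD with the 28-day condition on SD.

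For other disease types:

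- Label SD then progression as Stable to match 12.7.1, or amend the 12.7.1 sentence if two progression-free assessments are intended.
- Say which rule applies to CNS tumors with measurable disease (12.6.1, 12.6.3) and to neuroblastoma with measurable disease (Table 4).
- Do not leave PR or CR then progression ranked below SD then progression.

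The cost is one revised table and a short note on scope. Best response can be re-derived from assessments already recorded, with no extra scans or patients.

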12.7.2 Duration of Response

Duration of overall response: The duration of overall response is measured from the time measurement criteria are met for CR or PR (whichever is first recorded) until the first date that recurrent or progressive disease is objectively documented (taking as reference for progressive disease the smallest measurements recorded since the treatment started).

The duration of overall CR is measured from the time measurement criteria are first met for CR until the first date that progressive disease is objectively documented.

Duration of stable disease: Stable disease is measured from the start of the treatment until the criteria for progression are met, taking as reference the smallest measurements recorded since the treatment started, including the baseline measurements.

13.0 ADVERSE EVENT REPORTING REQUIREMENTS

Adverse event data collection and reporting which are required as part of every clinical trial, are done to ensure the safety of patients enrolled in the studies as well as those who will enroll in future studies using similar agents. Adverse events are reported in a routine manner at scheduled times during a trial. (Please follow directions for routine reporting provided in the Case Report Forms for this protocol). Additionally, certain adverse events must be reported in an expedited manner to allow for optimal monitoring of patient safety and care. The following sections provide information about expedited reporting.

Reporting requirements may include the following considerations: 1) whether the patient has received an investigational or commercial agent; 2) whether the adverse event is considered serious; 3) the grade (severity); and 4) whether or not hospitalization or prolongation of hospitalization was associated with the event.

An investigational agent is a protocol drug administered under an Investigational New Drug Application (IND). In some instances, the investigational agent may be available commercially, but is actually being tested for indications not included in the approved package label.

Commercial agents are those agents not provided under an IND but obtained instead from a commercial source. The NCI, rather than a commercial distributor, may on some occasions distribute commercial agents for a trial.

13.1 Steps to Determine If an Adverse Event Is To Be Reported In an Expedited Manner

Step 1: Identify the type of adverse event using the NCI CTCAE version 5.0. All appropriate treatment areas should have access to a copy of the CTCAE version 5.0. A copy of the CTCAE version 5.0 can be downloaded from the CTEP web site http://ctep.cancer.gov/protocolDevelopment/electronic_applications/ctc.htm.

Step 2: Grade the adverse event using the NCI CTCAE.

Step 3: Review Table A in this section to determine if:

- the adverse event is considered serious;
- there are any protocol-specific requirements for expedited reporting of specific adverse events that require special monitoring; and/or
- there are any protocol-specific exceptions to the reporting requirements.

NOTE: This includes all events that occur within 30 days of the last dose of protocol treatment. Any event that occurs more than 30 days after the last dose of treatment and is attributed (possibly, probably, or definitely) to the agent(s) must also be reported according to the instructions in the table below. Attribution categories are as follows: Unrelated, Unlikely, Possible, Probable, and Definite.

Table A: Phase 1 and Early Phase 2 Studies: Expedited Reporting Requirements for Adverse Events that Occur on Studies under an IND/IDE within 30 Days of the Last Administration of the Investigational Agent/Intervention ^{1,2}

FDA REPORTING REQUIREMENTS FOR SERIOUS ADVERSE EVENTS (21 CFR Part 312)

NOTE: Investigators **MUST** immediately report to the sponsor **ANY** Serious Adverse Events, whether or not they are considered related to the investigational agent(s)/intervention (21 CFR 312.64)

An adverse event is considered serious if it results in **ANY** of the following outcomes:

- 1) Death
- 2) A life-threatening adverse event
- 3) An adverse event that results in inpatient hospitalization or prolongation of existing hospitalization for ≥ 24 hours
- 4) A persistent or significant incapacity or substantial disruption of the ability to conduct normal life functions
- 5) A congenital anomaly/birth defect.
- 6) Important Medical Events (IME) that may not result in death, be life threatening, or require hospitalization may be considered serious when, based upon medical judgment, they may jeopardize the patient or subject and may require medical or surgical intervention to prevent one of the outcomes listed in this definition. (FDA, 21 CFR 312.32; ICH E2A and ICH E6).

ALL SERIOUS adverse events that meet the above criteria **MUST** be immediately reported via CTEP-AERS within the timeframes detailed in the table below.

Hospitalization	Grade 1 and Grade 2 Timeframes	Grade 3-5 Timeframes
Resulting in Hospitalization ≥ 24 hrs	7 Calendar Days	24-Hour 5 Calendar Days
Not resulting in Hospitalization ≥ 24 hrs	Not required	

NOTE: Protocol specific exceptions to expedited reporting of serious adverse events are found below under the section entitled "Additional Instructions or Exceptions."

Expedited AE reporting timelines are defined as:

- "24-Hour; 5 Calendar Days" - The AE must initially be reported via CTEP-AERS within 24 hours of learning of the AE, followed by a complete expedited report within 5 calendar days of the initial 24-hour report.
- "7 Calendar Days" - A complete expedited report on the AE must be submitted within 7 calendar days of learning of the AE.

¹Serious adverse events that occur more than 30 days after the last administration of investigational agent/intervention and have an attribution of possible, probable, or definite require reporting as follows:

Expedited 24-hour notification followed by complete report within 5 calendar days for:

- All Grade 3, 4, and Grade 5 AEs

Expedited 7 calendar day reports for:

- Grade 2 AEs resulting in hospitalization or prolongation of hospitalization

² For studies using PET or SPECT IND agents, the AE reporting period is limited to 10 radioactive half-lives, rounded UP to the nearest whole day, after the agent/intervention was last administered. Footnote "1" above applies after this reporting period.

Effective Date: May 5, 2011

- Any medical event equivalent to CTCAE Grade 3, 4, or 5 that precipitates hospitalization (or prolongation of existing hospitalization) must be reported regardless of attribution and designation as expected or unexpected with the exception of any events identified as protocol-specific expedited adverse event reporting exclusions.

- Use the NCI protocol number and the protocol-specific patient ID provided during trial registration on all reports.

Additional Instructions or Exceptions to CTEP-AERS Expedited Reporting Requirements for Phase 1 Trials Utilizing an Agent under a CTEP-IND or Non-CTEP IND:

- Any death that occurs more than 30 days after the last dose of treatment with an investigational agent which can be attributed (possibly, probably, or definitely) to the agent and is not clearly due to progressive disease must be reported via CTEP-AERS for an agent under a CTEP or non-CTEP IND agent per the timelines outlined in the table above.
- Myelosuppression, (Grade 1 through Grade 4 adverse events as defined in the table below), does not require expedited reporting, unless it is associated with hospitalization.

Category	Adverse Events
INVESTIGATIONS	Platelet count decreased
INVESTIGATIONS	White blood cell decreased
INVESTIGATIONS	Neutrophil count decreased
INVESTIGATIONS	Lymphocyte count decreased
BLOOD/LYMPHATICS DISORDERS	Anemia

- Grade 1 and 2 adverse events listed in the table below do not require expedited reporting via CTEPAERS, unless it is associated with hospitalization

Category	Adverse Events
GASTROINTESTINAL DISORDERS	Nausea
GASTROINTESTINAL DISORDERS	Vomiting
GASTROINTESTINAL DISORDERS	Diarrhea
GASTROINTESTINAL DISORDERS	Constipation
GASTROINTESTINAL DISORDERS	Decreased appetite
GASTROINTESTINAL DISORDERS	Abdominal distension
GASTROINTESTINAL DISORDERS	Stomatitis
GENERAL DISORDERS AND ADMINISTRATION SITE CONDITIONS	Fever
GENERAL DISORDERS AND ADMINISTRATION SITE CONDITIONS	Peripheral edema
GENERAL DISORDERS AND ADMINISTRATION SITE CONDITIONS	Fatigue
GENERAL DISORDERS AND ADMINISTRATION SITE CONDITIONS	Pain
INFECTIONS AND INFESTATIONS	Infection
INVESTIGATIONS	Alanine aminotransferase increased
INVESTIGATIONS	Aspartate aminotransferase increased
INVESTIGATIONS	Alkaline phosphatase increased
INVESTIGATIONS	GGT increased
INVESTIGATIONS	Blood bilirubin increased
INVESTIGATIONS	Creatinine increased
METABOLISM AND NUTRITION DISODERS	Dehydration
METABOLISM AND NUTRITION	Hypophosphatemia

DISORDERS	
MUSCULOSKELETAL AND CONNECTIVE TISSUE DISORDERS	Myalgia
MUSCULOSKELETAL AND CONNECTIVE TISSUE DISORDERS	Arthralgia
MUSCULOSKELETAL AND CONNECTIVE TISSUE DISORDERS	Muscle Spasms
NERVOUS SYSTEM DISORDERS	Dizziness
NERVOUS SYSTEM DISORDERS	Headache
NERVOUS SYSTEM DISORDERS	Peripheral neuropathy
NERVOUS SYSTEM DISORDERS	Paresthesia
PSYCHIATRIC DISORDERS	Anxiety
PSYCHIATRIC DISORDERS	Confusion
PSYCHIATRIC DISORDERS	Insomnia
RENAL AND URINARY DISORDERS	Dysuria
REPIRATORY, THORACIC AND MEDISTINAL DISORDERS	Cough
REPIRATORY, THORACIC AND MEDISTINAL DISORDERS	Nasal congestion
RESPIRATORY, THORACIC AND MEDIASTINAL DISORDERS	Dyspnea
REPIRATORY, THORACIC AND MEDISTINAL DISORDERS	Wheezing
SKIN AND SUBCUTANEOUS TISSUE DISORDERS	Night sweats
SKIN AND SUBCUTANEOUS TISSUE DISORDERS	Pruritus
SKIN AND SUBCUTANEOUS TISSUE DISORDERS	Rash

As referenced in the CTEP Adverse Events Reporting Requirements, an AE that resolves and then recurs during a subsequent cycle does not require CTEP-AERS reporting unless (1) the Grade increases; or (2) hospitalization is associated with the recurring AE.

